Appendix 1 Schedule of Assessments

Study Procedures	Both Arms	Arm A (Atezolizumab)	Arm B (Observation)			Both Arms	
	Screening for Randomization	All Cycles	Discontinuation ^a	Cycles 1, 3, 5, 7, 9, 11, 13, and 15	Cycles 2, 4, 6, 8, 10, 12, 14, and 16	Discontinuation ^a	
	Days –28 to –1	Day 1 (± 3 Days for Cycles ≥ 2) ^b	≤ 30 Days after Last Dose	Day 1 (± 3 Days for Cycles ≥ 2) ^b	Day 1 (± 3 Days) ^b	≤ 30 Days after Last Visit	Follow-Up
Signed Informed Consent Form(s) ^c	x						
Review of eligibility criteria	x						
Medical, surgical, and cancer histories, including demographic information ^d	x						
Pregnancy test ^e	x	x	x				
ECOG performance status	x	x ^f	x	x ^f		x	
Age-adjusted Charlson comorbidity index (ACCI)	x						
Complete physical examination ^g	x		x			x	
Limited physical examination ^g		x ^f		x ^f			
Weight	x	x	x	x		x	
Height	x						
Vital signs ^h	x	x	x	x		x	
12-lead electrocardiogram ⁱ	x	x	x				
HIV, HCV serology ^j	x						
Hematology ^k	x	x ^f	x	x ^f		x	
Serum chemistry ^l	x	x ^f	x	x ^f		x	
Coagulation panel (aPTT, INR)	x		x			x	

Appendix 1 Schedule of Assessments (cont.)

Study Procedures	Both Arms	Arm A (Atezolizumab)		Arm B (Observation)			Both Arms
	Screening for Randomization	All Cycles	Discontinuation ^a	Cycles 1, 3, 5, 7, 9, 11, 13, and 15	Cycles 2, 4, 6, 8, 10, 12, 14, and 16	Discontinuation ^a	Follow-Up
	Days -28 to -1	Day 1 (± 3 Days for Cycles ≥ 2) ^b	≤ 30 Days after Last Dose	Day 1 (± 3 Days for Cycles ≥ 2) ^b	Day 1 (± 3 Days) ^b	≤ 30 Days after Last Visit	
Urinalysis ^m	x	x ^{n,f}	x	x ⁿ		x	
TSH, free T3, free T4	x	x ^{o,f}	x				
Auto-antibody testing ^p		x	x				
Serum sample for ATA assessment		See Appendix 2					
Serum sample for PK sampling		See Appendix 2					
Blood samples for biomarkers		See Appendix 2					
Optional whole blood sample for RCR ^q		x ^q		x ^q			
Study drug infusion ^r		x					
Archival/screening FFPE tumor tissue specimen or 15 unstained slides ^s	x						
Fresh biopsy (mandatory sample ^t and optional RCR sample ^u)		At the time of radiographic confirmation of disease recurrence ^{t,u}					
Assessments for UC recurrence ^v	x	Every 12 weeks following randomization (± 7 days; at approximately every four cycles) in first 3 years; every 24 weeks (± 10 days) for Years 4 and 5; and at Year 6 (± 10 days), until death, disease recurrence, loss to follow-up, end of Year 6, or withdrawal of consent. After the primary analysis, patients in the first 3 years of the study may be assessed for tumor recurrence every 24 weeks.					
Concomitant medications ^w	x	x	x	x	x	x	

Appendix 1 Schedule of Assessments (cont.)

Study Procedures	Both Arms	Arm A (Atezolizumab)		Arm B (Observation)			Both Arms
	Screening for Randomization	All Cycles	Discontinuation ^a	Cycles 1, 3, 5, 7, 9, 11, 13, and 15	Cycles 2, 4, 6, 8, 10, 12, 14, and 16	Discontinuation ^a	Follow-Up
	Days –28 to –1	Day 1 (± 3 Days for Cycles ≥ 2) ^b	≤ 30 Days after Last Dose	Day 1 (± 3 Days for Cycles ≥ 2) ^b	Day 1 (± 3 Days) ^b	≤ 30 Days after Last Visit	
Adverse events ^x	x	x	x	x	x	x	
Telephone contact ^y					x		
Survival and anticancer therapy follow-up ^z							x
Patient-reported outcomes ^{aa}		x ^{bb}	x	x		x	x

Note: For Arm A, assessments scheduled on the days of study treatment infusions should be performed before the infusion unless otherwise noted.

- ^a Patients will be asked to return to the clinic for a discontinuation visit not more than 30 days after the decision to discontinue treatment/observation early, or after the end of the one-year treatment/observation period.
- ^b After five cycles have been completed, one cycle may be delayed by 1 week (i.e., 28 days instead of 21 days for one cycle) for one time to allow for vacations.
- ^c Written informed consent is required for performing any study-specific tests or procedures. Written informed consent (on the main study Informed Consent Form) can be obtained outside the 28 days screening period prior to randomization. Prior to signing the main consent form for the study, patients may specifically allow for the collection and testing of archival or fresh tumor tissue by signing the pre-screening consent form. Results of standard-of-care tests or examinations performed prior to obtaining informed consent and within 28 days prior to randomization (except where otherwise specified) may be used for screening assessments rather than repeating such tests.
- ^d Cancer history includes stage, date of diagnosis, and prior anti-tumor treatment. Demographic information includes sex, age, and self-reported race/ethnicity.
- ^e Serum pregnancy test (for women of childbearing potential, including women who have had a tubal ligation) must be performed and documented as negative within 14 days prior to Cycle 1 Day 1. Starting from Cycle 3, either serum or urine pregnancy test (positive urine test results will be confirmed with a serum pregnancy test) must be performed every two cycles during the study treatment, and as clinically indicated thereafter.
- ^f ECOG performance status, limited physical examination and local/central lab assessments may be obtained ≤ 96 hours before Day 1 of each cycle.

Appendix 1 Schedule of Assessments (cont.)

- ^g Complete and limited physical examinations are defined in Section 4.5.3.
- ^h Vital signs include heart rate, respiratory rate, blood pressures, and temperature and will be performed as standard of care if clinically indicated for patients randomized to the observation arm. For patients randomized to the atezolizumab treatment arm, for the first infusions of study drug, the patient's vital signs should be determined up to 60 minutes before the start of infusion, and if clinically indicated, during and 30 (\pm 10) minutes after the infusion. For subsequent infusions, vital signs will be recorded if clinically indicated or if symptoms occurred in the prior infusion.
- ⁱ ECG recordings will be obtained during screening and when clinically indicated during study. ECGs for each patient should be obtained from the same machine wherever possible. ECG recordings must be performed after the patient has been resting in a supine position for at least 10 minutes.
- ^j See Section 4.5.6 for serology tests. HIV testing to be performed in accordance with national and/or institutional guidelines. HBV DNA must be collected on or before Cycle 1, Day 1 in patients who have negative serology for hepatitis B surface antigen and positive serology for anti HBe.
- ^k Blood samples collected to monitor safety will be collected in patients randomized to both arms. Hematology consists of CBC, including RBC count, hemoglobin, hematocrit, WBC count with automated differential (neutrophils, lymphocytes, eosinophils, monocytes, basophils, and other cells), and platelet count. A manual differential can be done if clinically indicated. Refer to Section 4.1.1 for a list of laboratory results to be obtained within 14 days prior to the first dose of study treatment.
- ^l Serum chemistry includes BUN, creatinine, sodium, potassium, magnesium, chloride, bicarbonate, calcium, phosphorus, glucose, total bilirubin, ALT, AST, alkaline phosphatase, LDH, total protein, and albumin. Refer to Section 4.1.1 for a list of laboratory results to be obtained within 14 days prior to the first dose of study treatment.
- ^m Urinalysis (specific gravity, pH, glucose, protein, ketones, and blood).
- ⁿ On Day 1 of Cycle 3 and every two cycles thereafter.
- ^o On Day 1 of Cycle 5 and every four cycles thereafter.
- ^p Baseline sample to be collected on Cycle 1, Day 1 prior to the first dose of study treatment. For patients who show evidence of immune mediated toxicity, additional samples will be collected, and all samples will be analyzed centrally. Includes anti-nuclear antibody, anti-double stranded DNA, circulating anti-neutrophil cytoplasmic antibody, and perinuclear anti neutrophil cytoplasmic antibody.
- ^q Whole blood for DNA isolation will be collected from patients who have consented to optional RCR sampling at baseline (pre-dose C1D1). If, however, the RCR genetic blood sample is not collected during the scheduled visit, it may be collected as soon as possible (after randomization) during the conduct of the clinical study.

Appendix 1 Schedule of Assessments (cont.)

- ^r Patients in Arm A will receive their first dose of study drug the day of randomization if possible. If this is not possible, the first dose should occur no later than 7 days after randomization. The initial dose of atezolizumab treatment will be delivered over 60 (\pm 15) minutes. If the first infusion is well tolerated, all subsequent infusions may be delivered over 30 (\pm 10) minutes. Atezolizumab treatment may be continued for a maximum of 16 cycles (or 12 months, whichever occurs first) until disease recurrence, unacceptable toxicity, withdrawal of consent, or study termination by the Sponsor.
- ^s Tumor tissue from radical surgical resection should be of good quality based on total and viable tumor content (sites will be informed if the quality of the submitted specimen is inadequate to determine tumor PD-L1 status). Prior to signing the main consent form for the study, patients may specifically allow for the collection and testing of archival or fresh tumor tissue by signing the prescreening Informed Consent Form. After signing of the Informed Consent Form, retrieval and submission of archival tumor sample can occur outside the 28-day screening period.
- ^t All patients will undergo a mandatory tumor biopsy sample collection at the time of radiographic confirmation of disease recurrence (see Section 4.5.5). Acceptable samples include resections; core needle biopsies for deep tumor tissue or lymph nodes; or excisional, incisional, punch, or forceps biopsies for cutaneous, subcutaneous, or mucosal lesions. For core needle biopsy specimens, at least three cores should be submitted for evaluation. *After the primary analysis, a confirmatory tumor biopsy is optional at the time of disease recurrence.*
- ^u For patients who have consented to collection of optional biopsies on the Optional Collection of Samples for RCR Informed Consent Form, optional tumor biopsy samples may be collected by core needle or excisional/punch biopsy per investigator discretion. Optional biopsy tissue will be stored in the RCR. Not applicable for sites that have not been granted approval for RCR sampling.
- ^v Surveillance for tumor recurrence must include physical examination and imaging studies of the chest, abdomen, upper urinary tracts, and pelvis. Other examinations such as laboratory or urine cytology should be performed as clinically indicated. Recurrence assessment at Year 6 will be performed at approximately 48 weeks after the last one in Year 5. *Patients in Years 1–3 of the study may be assessed for tumor recurrence every 24 weeks.* See Section 4.5.5 for details of assessment requirements.
- ^w Concomitant medications include any prescription medications or over-the-counter medications. At screening, any medications the patient has used within the 7 days prior to written informed consent should be documented. At subsequent visits, changes to current medications or medications used since the last documentation of medications will be recorded.

Appendix 1 Schedule of Assessments (cont.)

- ^x After informed consent has been obtained but prior to randomization, only serious adverse events caused by a protocol-mandated intervention should be reported. Upon randomization into study, patients who experience a serious adverse event or protocol-defined adverse events of special interest will be followed for safety for 90 days following their last dose of study drug or until they receive another anti-cancer therapy, whichever comes first. Patients who experience all other adverse events will be reported for patients until 30 days after the last dose of study treatment (for Arm A) or the last day in the observation period (approximately Day 365 for Arm B), or until initiation of another anti-cancer therapy, whichever occurs first. After this period, investigators should ensure any deaths, serious adverse events, or other adverse events of concern are reported if they are later assessed to be related to atezolizumab treatment. The investigator should follow each adverse event until the event has resolved to baseline grade or better, the event is assessed as stable by the investigator, the patient is lost to follow up, or the patient withdraws consent. Every effort should be made to follow all serious adverse events considered to be related to atezolizumab treatment or trial-related procedures until a final outcome can be reported.
- ^y This clinic contact can be either via telephone call or formal clinic visit.
- ^z Survival follow-up information will be recorded via telephone calls, patient medical records, and/or clinic visits approximately every 3 months (± 7 days) from the completion or discontinuation of the treatment/observation period until death, loss to follow-up, or study termination by Roche. All patients (irrespective of which arm they are randomized to) will be followed for survival and new anticancer therapy information unless the patient requests to be withdrawn from follow-up; this request must be documented in the source documents and signed by the investigator. If the patient withdraws from study, the study staff may use a public information source (e.g., county records) to obtain information about survival status only. Patients who have completed the treatment or observation phase and continue in disease recurrence follow-up should have survival follow-up *in parallel* approximately every 3 months. All patients must still be followed for new anti-cancer therapy.
- ^{aa} The PRO questionnaire EQ-5D-5L will be completed by the patients at the investigational site. All PRO questionnaires are required to be administered prior to administration of study treatment (Arm A) and/or prior to any other study assessment(s) to ensure that the validity of the instrument is not compromised and to ensure that data quality meets regulatory requirements. Study personnel should review all questionnaires for completeness before the patient leaves the investigational site, and the hard copy originals of the questionnaires must be maintained as part of the patient's medical record when relevant at the site for source data verification. After discontinuation of the treatment/observation period, for patients who have not experienced disease recurrence, the EQ-5D-5L will be administered at the same schedule as the assessments for disease recurrence (see Section 4.5.5). The EQ-5D-5L will also be recorded at 6, 12, and 24 weeks after disease recurrence per telephone interview by trained site staff and in compliance with best practices and recommendations by EuroQol. Study personnel will record patient responses on a paper copy of the EQ-5D-5L during the telephone interview as record of source documentation. *After the primary analysis, the EQ-5D-5L assessments are no longer required for patients who are in disease recurrence follow-up or who have had a DFS event.*
- ^{bb} Odd-numbered cycles only (i.e., Cycles 1, 3, 5, 7, 9, 11, 13, and 15).

Appendix 2 Schedule of Pharmacodynamic and Pharmacokinetic Assessments

Study Visit	Time	Sample	Arm A	Arm B
Cycle 1, Day 1	Predose	Serum atezolizumab ATAs	x	
		Serum atezolizumab PK	x	
		PD biomarker ^a	x	x
	30 min (± 10 min) after end of atezolizumab infusion	Serum atezolizumab PK	x	
Cycles 2, 3, and 4, Day 1	Predose	Serum atezolizumab ATAs	x	
		Serum atezolizumab PK	x	
		PD biomarker (Cycle 3, Day 1 only) ^a	x	x
Cycles ≥8, Day 1, every 8 cycles starting Cycle 8	Predose	Serum atezolizumab ATAs	x	
		Serum atezolizumab PK	x	
At time of fresh biopsy (e.g., at the time of first radiographic confirmation of disease recurrence)		PD biomarker ^a	x	x
Treatment discontinuation visit	At visit	Serum atezolizumab ATAs	x	
		Serum atezolizumab PK	x	
		PD biomarker ^a	x	
120 days (± 30 days) after last dose of atezolizumab ^b	At visit	Serum atezolizumab ATAs	x	
		Serum atezolizumab PK	x	

ATAs=anti-therapeutic antibodies; PD=pharmacodynamics; PK=pharmacokinetics.

^a Pharmacodynamic samples may include plasma, serum, and whole blood (see laboratory manual for details on sample collection).

^b To be collected unless the patient withdraws consent or the study closes.

Appendix 3

Criteria for PD-L1 Diagnostic Assessment in Study WO29636

Description of IHC Scoring Algorithm	IHC IC score
Absence of any discernible PD-L1 staining OR Presence of discernible PD-L1 staining of any intensity in tumor-infiltrating immune cells (IC) covering < 1% of tumor area occupied by tumor cells, associated intratumoral, and contiguous peri-tumoral desmoplastic stroma	IHC IC0 (IC < 1%)
Presence of discernible PD-L1 staining of any intensity in tumor-infiltrating immune cells covering between $\geq 1\%$ to < 5% of tumor area occupied by tumor cells, associated intratumoral, and contiguous peri-tumoral desmoplastic stroma	IHC IC1 (5% > IC \geq 1%)
Presence of discernible PD-L1 staining of any intensity in tumor infiltrating immune cells covering between $\geq 5\%$ to < 10% of tumor area occupied by tumor cells, associated intratumoral, and contiguous peri-tumoral desmoplastic stroma	IHC IC2 (10% > IC \geq 5%)
Presence of discernible PD-L1 staining of any intensity in tumor infiltrating immune cells covering $\geq 10\%$ of tumor area occupied by tumor cells, associated intratumoral, and contiguous peri-tumoral desmoplastic stroma	IHC IC3 (IC \geq 10%)

Appendix 4 Age-Adjusted Charlson Comorbidity Index (ACCI) Worksheet

Weight	Comorbidity
1	Myocardial infarction Congestive heart failure Peripheral vascular disease or bypass Cerebrovascular disease or transient ischemic disease Dementia or Alzheimer's Chronic obstructive pulmonary disease Rheumatic or connective tissue disease Gastric or peptic ulcer Diabetes without end-organ damage Warfarin Depression Hypertension
2	Hemiplegia Mild liver disease Renal disease Diabetes with end-organ damage Any solid tumor, leukemia or lymphoma Skin ulcers/cellulitis
3	Severe liver disease
6	Metastatic solid tumor HIV or AIDS
1	For each decade over age 40

ACCI scores will be calculated by the method previously reported by Charlson et al. (1987), in which comorbid conditions are weighted and scored, with additional points added for age.

REFERENCE

Appendix 4 Age-Adjusted Charlson Comorbidity Index (ACCI) Worksheet (cont.)

Patient Number:	Patient Age:
-----------------	--------------

Condition	Weight	Calculate Score	Notes
1. Myocardial infarction	1		
2. Congestive heart failure	1		
3. Peripheral vascular disease or bypass	1		
4. Cerebrovascular disease or transient ischemic disease	1		CVA only
5. Hemiplegia	2		If hemiplegia, do not count CVA separately
6. Pulmonary disease/ asthma	1		
7. Diabetes	1		Diabetes only
7a. Diabetes with end organ damage	2		If end organ damage, do not count Diabetes separately
8. Renal disease	2		
9. Mild liver disease	2		
9a. Severe liver disease	3		
10. Gastric or peptic ulcer	1		
11. Cancer (lymphoma, leukemia, solid tumor)	2		Non-metastatic cancer only (other than UC)
11a. Metastatic solid tumor	6		If Metastatic, do not count cancer separately
12. Dementia or Alzheimer's	1		
13. Rheumatic or connective tissue disease	1		
14. HIV or AIDS	6		
15. Hypertension	1		
16. Skin ulcers/ cellulitis	2		
17. Depression	1		
18. Warfarin	1		

1 point for each decade over age 40 age 40 – 49 years = 0 age 50 – 59 years = 1 age 60 – 69 years = 2 age 70 – 79 years = 3 age 80 – 89 years = 4 age 90 – 99 years = 5	
---	--

TOTAL Score

--

ACCI scores will be calculated by the method previously reported by Charlson et al. (1987), in which comorbid conditions are weighted and scored, with additional points added for age.

REFERENCE

Appendix 5 Preexisting Autoimmune Diseases

Patients should be carefully questioned regarding their history of acquired or congenital immune deficiencies or autoimmune disease. Patients with any history of immune deficiencies or autoimmune disease are excluded from participating in the study. Possible exceptions to this exclusion could be patients with a medical history of such entities as atopic disease or childhood arthralgias where the clinical suspicion of autoimmune disease is low. Patients with a history of autoimmune-related hypothyroidism on a stable dose of thyroid replacement hormone may be eligible for this study. In addition, transient autoimmune manifestations of an acute infectious disease that resolved upon treatment of the infectious agent are not excluded (e.g., acute Lyme arthritis). Contact the Medical Monitor regarding any uncertainty over autoimmune exclusions.

Acute disseminated encephalomyelitis	Dysautonomia	Ord's thyroiditis
Addison's disease	Epidermolysis bullosa acquisita	Pemphigus
Ankylosing spondylitis	Gestational pemphigoid	Pernicious anemia
Antiphospholipid antibody syndrome	Giant cell arteritis	Polyarteritis nodosa
Aplastic anemia	Goodpasture's syndrome	Polyarthritis
Autoimmune hemolytic anemia	Graves' disease	Polyglandular autoimmune syndrome
Autoimmune hepatitis	Guillain-Barré syndrome	Primary biliary cirrhosis
Autoimmune hypoparathyroidism	Hashimoto's disease	Psoriasis
Autoimmune hypophysitis	IgA nephropathy	Reiter's syndrome
Autoimmune myocarditis	Inflammatory bowel disease	Rheumatoid arthritis
Autoimmune oophoritis	Interstitial cystitis	Sarcoidosis
Autoimmune orchitis	Kawasaki's disease	Scleroderma
Autoimmune thrombocytopenic purpura	Lambert-Eaton myasthenia syndrome	Sjögren's syndrome
Behcet's disease	Lupus erythematosus	Stiff-Person syndrome
Bullous pemphigoid	Lyme disease – chronic	Takayasu's arteritis
Chronic fatigue syndrome	Mooren's ulcer	Ulcerative colitis
Chronic inflammatory demyelinating polyneuropathy	Morphea	Vitiligo
Churg-Strauss syndrome	Multiple sclerosis	Vogt-Kovanagi-Harada disease
Crohn's disease	Myasthenia gravis	Wegener's granulomatosis
Dermatomyositis	Neuromyotonia	
	Opsoclonus myoclonus syndrome	
	Optic neuritis	

Appendix 6 Anaphylaxis Precautions

EQUIPMENT NEEDED

- Tourniquet
- Oxygen
- Epinephrine for subcutaneous, intravenous, and/or endotracheal use in accordance with standard practice
- Antihistamines
- Corticosteroids
- Intravenous infusion solutions, tubing, catheters, and tape

PROCEDURES

In the event of a suspected anaphylactic reaction during study drug infusion, the following procedures should be performed:

1. Stop the study drug infusion.
2. Apply a tourniquet proximal to the injection site to slow systemic absorption of study drug. Do not obstruct arterial flow in the limb.
3. Maintain an adequate airway.
4. Administer antihistamines, epinephrine, or other medications as required by patient status and directed by the physician in charge.
5. Continue to observe the patient and document observations.

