- PD-L1 IHC status (IHC score of IC0/1 vs. IHC score of IC2/3)
- Prior neoadjuvant chemotherapy (yes vs. no)

[figure not shown]
Randomization must occur within 14 weeks after surgical resection of the primary tumor, and study drug administration should begin within 7 calendar days after randomization.

For patients in Arm A, atezolizumab will be administered intravenously (IV) on Day 1 of each 21-day cycle for 16 cycles (up to 1 year). In Arm B, patients will continually undergo observation starting on Day 1 of each 21-day cycle for 16 cycles (up to 1 year). Treatment/observation will be discontinued in the event of disease recurrence, unacceptable toxicity, withdrawal of consent, or study termination by the Sponsor.

To ensure the same frequency of study assessments between the treatment arms, including assessments for disease recurrence and safety, patients in Arm B will be required to undergo q3w medical contacts for assessments during the first year, which will consist of formal clinic visits alternating with clinical contacts (either via telephone call or formal outpatient clinic visit) for symptom and adverse event assessment.

Patients in the control arm will not be allowed to cross over to receive atezolizumab treatment within this study.

Figure 3 Study Schema

UC = urothelial carcinoma.

All patients will undergo scheduled assessments for tumor recurrence at baseline and every 12 weeks (approximately every 4 cycles) in the first year following randomization. Upon completion of the treatment/observation period, surveillance for tumor recurrence will be performed every 12 weeks for Years 2–3; every 24 weeks for Years 4–5; and at Year 6 (approximately 48 weeks after the last assessment in Year 5). *After the primary analysis, patients in Years 2–3 of the study may be assessed for tumor recurrence every 24 weeks.* In the absence of a DFS event (see definition in Section 3.4.1.1), surveillance for tumor recurrence should continue regardless of whether patients start new anticancer therapy, until withdrawal of consent, loss to follow-up, or study termination by the Sponsor, whichever occurs first. For patients with muscle-invasive bladder cancer

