4.3.2 Dosage, Administration, and Compliance

4.3.2.1 Atezolizumab

The dose level of atezolizumab to be tested in this study is 1200 mg (equivalent to an average body weight–based dose of 15 mg/kg) administered by IV infusion q3w (21 [\pm 3] days) \times 16 cycles or 1 year (whichever occurs first).

Administration of atezolizumab will be performed in a setting with emergency medical facilities and staff who are trained to monitor for and respond to medical emergencies. For further details, see the Atezolizumab Pharmacy Manual and Investigator's Brochure.

Atezolizumab infusions will be administered per the instructions outlined in [Table 7](#).

Table 7 Administration of First and Subsequent Infusions of Atezolizumab

First Infusion	Subsequent Infusions

 • No pre-medication is allowed. • Record patient’s vital signs (heart rate, respiratory rate, blood pressure, and temperature) within 60 minutes before starting infusion. • Infuse atezolizumab (one vial in 250 mL NaCl) over 60 (± 15) minutes. • Record patient’s vital signs during the infusion and/or 30 minutes (± 10) after the infusion if clinically indicated. • Patients will be informed about the possibility of delayed post-infusion symptoms and instructed to contact their study physician if they develop such symptoms. 	
 • If patient experienced infusion-related reaction during any previous infusion, pre-medication with antihistamines may be administered for Cycles ≥ 2 at the discretion of the treating physician. • If the patient tolerated the first infusion well without infusion-associated adverse events, the second infusion may be delivered over 30 (± 10) minutes. • If the patient had an infusion-related reaction during the previous infusion, the subsequent infusion must be delivered over 60 (± 15) minutes. • If clinically indicated or patient experienced symptoms during the previous infusion, record patient’s vital signs (heart rate, respiratory rate, blood pressure, and temperature) within 60 minutes before starting infusion, during the infusion and/or 30 minutes (± 10) after the infusion. • If no reaction occurs, continue subsequent infusions over 30 (± 10) minutes with same schedule for recording vital signs.

NaCl = sodium chloride.

For anaphylaxis precautions, see [Appendix 6](#).

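### Appendix 6, step 2 calls for a tourniquet to slow absorption of a drug that is given only intravenously and has already been stopped; the step should be deleted

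*Protocol*

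**What the plan says.** Protocol Appendix 6 gives five numbered steps for a suspected anaphylactic reaction during study drug infusion:

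- Step 1 has staff halt the infusion.
- Step 2 reads: "Apply a tourniquet proximal to the injection site to slow systemic absorption of study drug. Do not obstruct arterial flow in the limb".
- Step 3 is to keep the airway adequate.
- Step 4 reads: "Administer antihistamines, epinephrine, or other medications as required by patient status and directed by the physician in charge".
- Step 5 is to keep observing the patient and document what is seen.

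The equipment list includes a tourniquet, IV solutions and catheters, and "Epinephrine for subcutaneous, intravenous, and/or endotracheal use in accordance with standard practice". Step 2 is the only use the protocol gives for the tourniquet.

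Atezolizumab is the only investigational product (Section 4.3), and Sections 3.1 and 4.3.2.1 give it by IV infusion and no other route. Table 7 in Section 4.3.2.1 says of the first infusion: "Infuse atezolizumab (one vial in 250 mL NaCl) over 60 (± 15) minutes". If that is well tolerated, "the second infusion may be delivered over 30 (± 10) minutes", and later infusions may keep that duration. The same section requires dosing where there are emergency facilities and "staff who are trained to monitor for and respond to medical emergencies".

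Sections 4.3.2.1, 4.4.2, 5.1.1 and 5.1.4 send sites to Appendix 6 for anaphylaxis. Section 4.4.1 does so for serious infusion-associated events.

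**The concern.** The stated purpose of step 2 needs drug that has been deposited at a site and is still being absorbed, as after a subcutaneous or intramuscular injection. A drug infused into a vein is already in the circulation, so the reason given for the tourniquet does not fit this product.

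Two features make this more than loose wording. The step is second in an emergency list, ahead of the airway and of epinephrine. And its reference to the limb means it can be carried out only when venous access is in a limb. In that case constricting the veins above the access point can impede epinephrine or fluids given through the same line. What is at stake is the quality of an emergency instruction that five sections point to; no trial result depends on it.

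**Working it through.** The plan gives no figure to reproduce. The check sets the text of step 2 against the dosing sections, then bounds the amount of drug a tourniquet could still hold back.

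**Text.** The trigger is a reaction during infusion (Appendix 6). The route is IV only (Sections 3.1 and 4.3.2.1). The infusion has stopped before step 2 begins (step 1). No section describes a depot route. What could remain in the limb is drug still passing through its veins, plus any that has leaked outside the vein.

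**Delivery rate.** Inputs: 1200 mg per dose (Section 4.3.2.1) and the durations in Table 7 of that section. Rate = 1200 mg / duration; percentage per minute = rate / 1200.

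| Infusion | Permitted duration | Rate | Share of dose per minute |
|---|---|---|---|
| First, 60 ± 15 min | 45 to 75 min | 1200/75 = 16 to 1200/45 = 26.7 mg/min | 1.3% to 2.2% |
| Later, 30 ± 10 min | 20 to 40 min | 1200/40 = 30 to 1200/20 = 60 mg/min | 2.5% to 5.0% |

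**Drug in the limb veins when the infusion stops.** The documents give no transit time; 10 to 60 seconds is assumed here. Amount = rate × transit time.

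- Slowest infusion, shortest transit: 16 × 10/60 = 2.7 mg, or 0.2% of the dose.
- Fastest infusion, longest transit: 60 × 60/60 = 60 mg, or 5.0% of the dose.

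The amount falls while the tourniquet is being put on. If that takes as long as the assumed transit, none of this drug is left to hold back. Leaked drug is not counted.

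**Who could be affected.**

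- Only Arm A is dosed: 800 / 2 = about 400 patients.
- The first dose comes no later than 7 days after randomization, and treatment is capped at 16 cycles or 12 months, whichever is earlier (Appendix 1, footnote r). Section 5.1.3 allows doses to be held, so the calendar cap is the firm bound: 7 + 365 = Day 372 if the year runs from the first dose.
- Section 6.1.2 projects accrual to end at Month 32, so dosing ends at about Month 32 + 12 = 44. The primary DFS analysis is projected at Month 50, 50 − 44 = 6 months later.
- Section 6.1.2 also requires at least 12 months after the last enrollment before that analysis, so on these rules dosing is over, to within about a week, before the analysis can take place.

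**The case against.** **It may no longer matter.** Much of the new text in protocol version 10 relaxes procedures after the primary analysis, by which time dosing should be finished. A correction would come in an amendment later still. This is a strong point, and it is why the number affected may be nil. It is not proof, because the text available does not show when version 10 took effect. Version 10 also adds new infusion-reaction and cytokine-release guidance in Appendix 9, so the sponsor was still maintaining acute infusion-safety text.

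**The lack of benefit is a clinical inference.** No section says that the tourniquet is useless or that it impedes rescue. That is true. The mismatch between the stated purpose and the IV route can, however, be read directly from the documents.

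**Percent of dose may be the wrong yardstick.** Section 4.3.2.1 equates 1200 mg with 15 mg/kg, so 60 mg is 60/1200 × 15 = 0.75 mg/kg, while the Phase Ia study gave doses from 0.01 mg/kg (Section 1.2.2.2). A small amount could matter in anaphylaxis. This stands as a limit on the arithmetic, which bounds how much drug is involved and not its clinical effect. The 5.0% end also applies only to 20-minute infusions after a well-tolerated first one.

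**The harm is conditional.** Step 2 protects arterial flow, step 4 leaves medication to the physician in charge, epinephrine may be given subcutaneously or endotracheally, new access can be placed, and trained staff are present. Nothing says step 2 must be completed before the airway is managed. All of this stands and lowers the expected harm. None of it supplies a reason to keep the step.

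No conflict with another section is claimed. Section 4.4.1 itself refers to Appendix 6, and Table 7 of Appendix 9 covers infusion-related reactions and cytokine-release syndrome, not anaphylaxis.

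**Conclusion.** The concern holds: step 2 is wrong as written, and minor. Its stated mechanism does not apply to an IV drug that has already been stopped, so little or no benefit is expected beyond briefly holding back drug in the limb veins or drug leaked outside the vein. Confidence is high that the text does not fit the route; no actual harm is claimed, and no section shows that treatment has been delayed. The estimate of residual drug depends on the assumed transit time, and any harm depends on rescue being given through the same limb line. The change is worth making because it alters what sites are told to do in an emergency and modestly favors patient safety.

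**What to change.** Delete step 2 of Appendix 6 and renumber the remaining steps. Reword step 1 along the lines of: stop the study drug infusion and maintain IV access. Airway and medication then follow directly. Keep the tourniquet on the equipment list, with obtaining venous access as its stated purpose; the protocol does not currently give that use, but it fits the IV solutions and catheters listed beside it. The sponsor's clinicians should confirm the final wording.

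The cost is a short text change carried in the next amendment; a stand-alone amendment is not needed. Section 9.6 requires IRB/EC approval, and regulatory approval where locally required, before the change is implemented, across about 200 sites (Section 9.4). If any patient is still being dosed, add a site notice. There is no statistical cost.
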